### 3.2.2 Secondary Endpoints

#### Immunogenicity Endpoints

Immune responses against *N. meningitidis* serogroup B\* test strains and *N. meningitidis* serogroups A, C, W-135, and Y, as measured by hSBA, 1 month after the first vaccination in all groups (except for subjects in the MenACWY group)

- hSBA GMTs against each of the *N. meningitidis* serogroup B test strains and against *N. meningitidis* serogroups A, C, W-135, and Y
- hSBA GMTs against all of *N. meningitidis* serogroup B test strains (pooled)
- Percentage of subjects with hSBA titers  $\geq$  the LLOQ against each of the *N. meningitidis* serogroup B test strains and against *N. meningitidis* serogroups A, C, W-135, and Y
- Percentage of subjects with a 4-fold increase in hSBA titers against *N. meningitidis* serogroups B test strains and against *N. meningitidis* serogroups A, C, W-135, and Y
- hSBA GMRs against each of the *N. meningitidis* serogroup B test strains and against *N. meningitidis* serogroups A, C, W-135, and Y at 1 month after the first vaccination against baseline (Day 1)

\*Serogroup B tests strains that will be tested are M14459 (fHbp), 96217 (NadA), NZ98/254 (PorA), and M07-0241084 (NHBA).

Note: a 4-fold rise is defined in the same way as described for the primary endpoints in Section 3.2.1.

The ratios of GMTs between study groups will be analyzed to evaluate effect of treatment as described below:

- a. Immune interference due to stress to lymph nodes (lymph-node effect) in rMenBOMV+ACWY\_S versus rMenBOMV+ACWY\_D study groups, on the pooled B strains, and individually by serogroup A, C, W-135, Y, and B test strains.
- b. Other unknown interference in MenABCWY versus rMenBOMV+ACWY\_S study groups, by serogroup A, C, W-135, Y, and B test strains.
- c. The difference in immune response compared to control groups in rMenBOMV+ACWY\_S versus rMenBOMV, rMenBOMV+ACWY\_D versus rMenBOMV, and MenABCWY versus rMenBOMV study groups, by serogroup B test strains.

### Safety Endpoints

- Solicited local and systemic AEs in all study groups
  - Occurrence of solicited local and systemic AEs during the 7 days (including the day of vaccination) after each vaccination (Day 1 to Day 7 and Day 61 to Day 67, Day 1 to Day 7 only for subjects in the MenACWY group)
- Unsolicited AEs in all study groups
  - Occurrence of unsolicited AEs during the 30 days (including the day of vaccination) after each vaccination (Day 1 to Day 31 and Day 61 to Day 91, Day 1 to Day 31 only for subjects in the MenACWY group)
- SAEs, medically attended AEs, AEs leading to withdrawal, and AESIs, in all study groups from informed consent signature to Visit 4 (Day 91)

## 4 General Statistical Considerations

Treatments will be labelled on all outputs as described in Table 2.

**Table 2 Treatment Labels**

Treatment Number	Treatment Label
P	MenABCWY
P	rMenBOMV+ACWY_S 
P	rMenBOMV+ACWY_D 
P	rMenBOMV
P	MenACWY

S = same arm approximately 2.5cm apart, D= different arms

Categorical data will be described using the subject count and percentage in each category. A row denoted ‘Missing’ will be displayed to account for missing values categorical summaries. The ‘Missing’ row will only be displayed if at least one study group has a non-zero count for this category. Note percentages will not be displayed in the ‘Missing’ row, to draw attention to the percentages for the non-missing categories. Unless specified otherwise, percentages will be based on the number of subjects in each study group within the analysis population. Percentages will not be displayed if the count for a study group is zero, in order to draw attention to the percentages for non-zero counts. Percentages will be displayed using one decimal place.

Continuous data will be described using descriptive statistics (i.e. n, mean, standard deviation, minimum and maximum). For the summary statistics of all numerical variables unless otherwise specified, minimum and maximum will be displayed to the same level of precision as reported. Mean will be displayed to one level of precision greater than the data collected. Standard deviation/standard error will be displayed to two levels of precision greater than the data collected. P-values will be rounded to three decimal places. If a p-value is less than 0.001 it will be reported as “<0.001” If a p-value is greater than 0.999 it will be reported as “>0.999”.

If statistical analysis cannot be performed for a particular serogroup or study group, then these should be displayed as “NC.” (not calculated). Confidence intervals that cannot be calculated should be displayed as “(NC.)”.

Data will be displayed in all listings sorted by study group. Subjects will be identified in the listings by the subject identification number.

Serogroups should be displayed in the order in Table 3. If the combined B serogroups are to be presented in a table or listing, this group should be displayed last.

**Table 3 Serogroup Display Order**

Serogroup (strain)	Display Order
Serogroup B (M14459)	1
Serogroup B (M07-0241084)	2
Serogroup B (96217)	3
Serogroup B (NZ98/254)	4
Serogroup C	5
Serogroup Y	6
Serogroup W-135	7
Serogroup A	8

Baseline will be defined as the value recorded at Visit 1. The study day will be calculated as assessment date - first dose date of study vaccine + 1 if the study date is on or after first dose date of study vaccine, or assessment date – first dose date of study vaccine if the study date is prior to the first dose date of study vaccine.

Throughout the study, logarithmic transformations and anti-logarithms will use base 10.

Statistical analysis will be performed using SAS® Version 9.3 or higher. Standardized and validated SAS macros from PPD will be used to set up table, listing, figure (TLF) formats (headers/footers and tabulation format) and tabulate the summaries. All tables and listings will be independently validated using double programming; datasets behind the figures will be independently validated using double programming and figure outputs will be independently validated manually.

#### **4.1 Sample Size**

Sample size calculation was performed using PASS 12 and SAS 9.2 (SAS Institute Inc., Cary, NC, USA). Values used in sample size calculation are based on previous study MenABCWY-011 (V102\_15). Because of the consistent decrease in GMT ratios in the MenABCWY group in comparison to the rMenBOMV group across the 4 serogroups in this previous study, the presence of the lymph-node effect will be tested globally on all the serogroups together.

The sample size is for exploratory statistical analysis purposes only. There are no formal confirmatory hypotheses to be tested. The text in this section describes what can be observed with the current sample size.

The potential immune interference due to immunological stress to lymph nodes is assumed to result in decreases to all of the 4 B test strains but to various extents. The sample size calculation shows that with a power range of 80% to 90%, a global lymph-node effect is detectable when the GMT ratio is between 64% (approximately -0.19 on log10 scale) and 74% (-0.13) pooling 4 variants of B test strains together and using a 1-sided false-positive error rate of 10%.

Assuming a rare event occurring at the rate of 1 out of 100, a sample size of 500 subjects in the study will have a probability of 99.3% to detect a rare AE.

A total of approximately 500 subjects (approximately 100 subjects in each group) are planned for enrollment into the study.

#### **4.2 Randomization, Stratification, and Blinding**

Randomization will be performed within 5 days prior to or at Visit 1 (Day 1). The randomization list will be generated using MATerial Excellence (MATEX). Central randomization will be performed using the Source DataBase for Internet Randomization (SBIR) system. Within each age stratum (10 to 17 years and 18 to 25 years) the randomization algorithm will use a minimization procedure accounting for center.

This is an open-label study. Only the laboratory in charge of the laboratory testing will be blinded to the treatment, subject, and visit number, and codes will be used to link the subject, visit, and study (without any link to the treatment attributed to the subject) to each sample.

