**Table 2 Study groups and treatment foreseen in the study**

Treatment name	Vaccine name	Study groups				
		MenABCWY	rMenBOMV +ACWY_S 	rMenBOMV +ACWY_D 	rMenBOMV	MenACWY
MenABCWY	MenACWY lyo	x				
	rMenB+OMV NZ					
rMenB+OMV NZ	rMenB+OMV NZ		x	x	x	
MenACWY	MenA lyo		x	x		x
	MenCWY liquid					

S refers to administration in the same arm (approximately 2.5 cm apart).

D refers to administration in 2 different arms.

- Control: active control
- Vaccination schedules: First vaccination at Visit 1 (Day 1) and second vaccination at Visit 3 (Day 61), with the exception of the MenACWY study group, which will have only 1 vaccination at Visit 1 (Day 1)
- Treatment allocation: Randomization will be performed prior to or at Visit 1 (Day 1). The randomization list will be generated using MATerial EXcellence (MATEX). Central randomization will be performed using the Source DataBase for Internet Randomization (SBIR) system.
- Blinding: Open-label

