### **5.3. Method of blinding**

This will be an open-label study.

The laboratory in charge of the laboratory testing will be blinded to the treatment, subject, and visit number, and codes will be used to link the subject, visit, and study (without any link to the treatment attributed to the subject) to each sample.

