**Table 4 List of study procedures**

Epoch	Epoch 001					
Type of contact	Visit 1	Safety call 1	Visit 2	Visit 3	Safety call 2	Visit 4
Time points	Day 1	Day 15	Day 31	Day 61	Day 75	Day 91
Sampling time points	Pre-Vacc 1		Post-Vacc 1			Post-Vacc 2
Informed consent	● 					
Check inclusion/exclusion criteria	● 			○		
Collect demographic data	● 					
Medical history	● 					
History directed physical examination	○					
Physical examination	○			○		
Urine pregnancy test	● 			● 		
Check contraindications and warnings and precautions to vaccination	●			● 		
Pre-vaccination body temperature	●			● 		
Measure/record height and weight	● 					
Study group and treatment number allocation	●					
Recording of administered treatment number	●			● 		
Blood sampling (~20 mL)	● 		●			● 
Vaccine(s) administration	●			● 		
Record any concomitant medications/vaccinations	●	●	●	● 	● 	● 
Record any intercurrent medical conditions	●	●	●	● 	● 	● 
Distribution of pDiary	○			○ 4,6		
Review of pDiary			○	○ 4		○ 4
Return of pDiary			○ 6	○ 4,6		○ 4,6
Recording of AEs within 30 minutes post-vaccination	●			● 		
Recording of solicited AEs (days 1 to 7 post-vaccination)	●			● 		
Recording of unsolicited AEs (days 1 to 30 post-vaccination)	●	●	●	● 	● 	● 
Recording of AEs, SAEs, medically attended AEs, AESI, and AEs leading to withdrawal	● 	●	●	●	●	●
Recording of AEs/SAEs related to study participation or to a concurrent GSK medication/vaccine	● 	●	●	●	●	●
Recording of SAEs related to study vaccine(s)	● 	●	●	●	●	●
Study conclusion						●

Activities that can be performed at a separate visit before Visit 1 (maximum 5 days before the Visit 1). All AEs/SAEs, including those related to study participation or to a concurrent GSK medication/vaccine should be recorded starting from informed consent signature. Inclusion/exclusion criteria should be re-checked prior to vaccination at Visit 1.

For women of childbearing age. The pregnancy test is to be performed locally onsite.

A pregnancy test is mandatory even if performed during a prior separate visit.

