### **9.3. Screen failures**

Screen failures are subjects who withdraw or are withdrawn from the study following informed consent, but before randomization to study treatment. Information relative to screen failures will be documented on the Screening Conclusion page/screen of the eCRF. The investigator will document whether the screen failure decision was made by the subject himself/herself, by the subject's parent(s)/LAR(s), or by the investigator, as well as which of the following possible reasons was responsible for the screen failure:

- Consent withdrawal, not due to an SAE
- Eligibility criteria not fulfilled (inclusion and exclusion criteria)
- Lost to follow-up
- Migrated or moved from the study area
- Other (specify)
- Protocol violation

- SAE not related to study participation or to a GSK concurrent medication
- SAE related to study participation or to a GSK concurrent medication

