**Figure 1 Study Design**

The duration of the study is up to 91 days with subjects attending 4 visits, 30 days apart, starting at Visit 1 (Day 1) and ending at Visit 4 (Day 91). Whenever possible, the investigator should arrange study visits within the intervals described in Table 1. Visits that occur outside of the intervals will be categorized as significant protocol deviations leading to the exclusion of a subject from one of the Per Protocol sets (PPSx).

A detailed list of study procedures can be found in Section 11.2.

The signed/witnessed/thumb printed informed consent of the subject/subject's parent(s)/legally acceptable representative(s) (LARs) must be obtained before study participation. The signed informed assent of the subject below the age of consent (i.e. minor) should be obtained in addition to the signed informed consent by his/her parent(s)/LAR(s) according to local rules and regulations.

On Visit 1 (Day 1) or up to 5 days before Visit 1 (where allowed according to Table 1) informed consent will be obtained and pre-vaccination procedures will be carried out. Upon satisfactory completion of pre-vaccination procedures, subjects will be allocated a study group and treatment number and will have blood samples drawn before receiving the first dose of study vaccine(s).

Subjects will be observed closely for at least 30 minutes following the administration of the vaccine(s), with appropriate medical treatment readily available in case of anaphylaxis. Solicited adverse events (AEs) will be recorded during this 30 minute period (see Section 9.1.1 for details of solicited AEs).

Subjects will have a second dose of study vaccine(s) administered at Visit 3 (with the exception of the MenACWY group who only receive a single dose at Visit 1) following satisfactory completion of pre-vaccination procedures. Subjects will have blood drawn at Visit 1, Visit 2 and Visit 4 (with the exception of the MenACWY group who will only have blood drawn at Visit 1 and Visit 2) to test for immune response within the serogroups.

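### The plan contradicts itself on when open-label randomisation may occur; if the pre-Visit 1 slot is used, eligibility re-check, pre-vaccination checks and baseline blood all follow knowledge of the group

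*SAP*

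**What the plan says.** Two sets of statements disagree.

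**Allocation may precede Visit 1.** SAP 4.2: "Randomization will be performed within 5 days prior to or at Visit 1 (Day 1". The treatment-allocation item in protocol section 3, repeated in the synopsis, reads "Randomization will be performed prior to or at Visit 1 (Day 1" and sets no limit in days.

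**Allocation is at Visit 1.** In protocol Table 4 and SAP Table 10 the row "Study group and treatment number allocation" is marked at Visit 1 and does not carry footnote 1, which identifies what may be done at a separate visit up to 5 days earlier. Protocol 5.2.2.1.1 has the vaccinating staff access the randomisation system once eligibility has been checked. SAP 3.1 says: "Upon satisfactory completion of pre-vaccination procedures, subjects will be allocated a study group and treatment number and will have blood samples drawn before receiving". That sentence names allocation ahead of the baseline draw.

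On the surrounding rules, protocol 5.3 says "This will be an open-label study"; only the laboratory is blinded. Footnote 1 to Table 4 adds "Inclusion/exclusion criteria should be re-checked prior to vaccination at Visit 1". Protocol 9.3 says "Screen failures are subjects who withdraw or are withdrawn from the study following informed consent, but before randomization to study treatment". Protocol 9.2 rules out replacement of withdrawn subjects.

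**The concern.** In an open-label trial, every step between allocation and first dose is a point at which the subject or the investigator can act on the assignment. Burden differs visibly between groups, from one injection in total to two at each of two visits, so a reluctant subject may decline, or a borderline check may be judged differently, depending on the group.

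All four full analysis sets are drawn from the All Exposed Set, which requires a vaccination, and the per-protocol sets are subsets of them. A subject allocated but not dosed is therefore in none, and no sensitivity analysis brings that subject back. The baseline draw matters separately. The primary contrasts use PPS3, which rests on FAS3 and needs a baseline result. A draw refused once the group is known removes the subject from the primary analysis even if the vaccine is given.

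**Working it through.** **Step 1. What follows allocation under each reading.**

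| Step | Source | Allocation before Visit 1 | Allocation at Visit 1, SAP 3.1 order |
|---|---|---|---|
| Initial eligibility check | Protocol 5.2.2.1.1 | before | before |
| Eligibility re-check | Table 4, footnote 1 | after | before, if counted as a pre-vaccination procedure |
| Pregnancy test on day of vaccination | Protocol 4.2 | after | before |
| Contraindications, temperature | Protocol 5.6.7, 5.6.8 | after | before |
| Baseline blood | Table 4, footnote 5 | after | after |

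SAP 3.1 does not settle the conflict. It lets pre-vaccination procedures take place up to 5 days early and allocates once they are complete. For what is allowed early it refers to SAP Table 1, which lists only visit intervals.

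**Step 2. Which contrasts are exposed.** Total injections per subject from SAP Table 5: MenABCWY 1 + 1 = 2; same-arm (S) 2 + 2 = 4; different-arm (D) 2 + 2 = 4; rMenBOMV 1 + 1 = 2; MenACWY 1. Of the eight contrasts in SAP Table 6, S versus D (4 and 4) and MenABCWY versus rMenBOMV (2 and 2) have equal counts. The other six differ: 2 and 4, 4 and 2, 4 and 1, 4 and 2, 4 and 1, 2 and 1.

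**Step 3. The plan's own power figure.** Inputs from protocol 10.4: 100 per group, difference 0.130 log10, SD 0.435, 1-sided alpha 10%, two-sample t-test. Noncentrality = 0.130 / (0.435 × √(2/100)) = 0.130 / 0.0615 = 2.11. Power by the noncentral t is 0.796, matching Table 14.

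**Step 4. Illustration of equal loss.** The documents give no rate of pre-dose loss. Assume 5 subjects lost per group and not made up: noncentrality = 0.130 / (0.435 × √(2/95)) = 2.06, power 0.780.

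**Step 5. Illustration of unequal loss.** Assume one group loses an excess fraction L, and those lost would have differed from those retained by k SDs. The retained mean moves by L × k × 0.435.

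- L = 2%, k = 0.25: 0.02 × 0.25 × 0.435 = 0.0022 log10, a GMT-ratio factor of 10^-0.0022 = 0.995, and 0.0022 / 0.130 = 1.7% of the planned effect.
- L = 5%, k = 0.5: 0.05 × 0.5 × 0.435 = 0.0109 log10, a factor of 0.975, and 8.4% of the planned effect.

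If such a shift ran against S in the S versus D test, the nominal 10% false-positive rate, Φ(shift / 0.0615 − 1.2816), would become 10.6% to 13.5%. L and k are assumptions throughout.

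**The case against.** The strongest reply is that the text directing sites already points to Visit 1: the tables withhold the early-activity footnote from allocation, the vaccinating staff operate the randomisation system, and protocol 5.6 lists the pregnancy test, contraindications and temperature ahead of allocation. That stands in part. A reader might infer that early allocation is the operating rule, and the documents do not support that. They conflict, and section 5.6 is a list rather than a stated sequence. Nor may one infer that subjects are randomised without any eligibility check: an initial check comes first, and only the re-check can follow.

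A reader might also infer that these losses disappear from the report. They do not. SAP 5.1 summarises the All Enrolled Set by group, including how many were vaccinated and the primary reason for withdrawal. SAP 7.2.1 gives, by group and visit, those not fully vaccinated, with reasons. The gap is confined to the immunogenicity sets, where an undosed subject has no post-vaccination response to analyse in any case.

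The illustration uses the S versus D effect and SD, yet S and D receive the same vaccines, injections and visits and differ only in one arm or two. Differential loss is hard to argue there. This objection stands. So do the points that titres are read blind, that the analyses are declared exploratory and descriptive, and that the group remains known through Day 91 whatever is changed.

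**Conclusion.** The inconsistency is real and should be resolved. The pre-Visit 1 permission opens an avoidable route for group-dependent loss before dose 1, and the allocation-then-blood order in SAP 3.1 leaves a smaller one even at Visit 1. The bias is probably small and cannot be sized from the documents. The shift of 0.002 to 0.011 log10 and the drop in power from 0.796 to 0.780 rest wholly on assumed loss rates and titre differences, and show only the order of magnitude. The route is more plausible for the six contrasts with unequal injection counts than for S versus D, so this point does not undermine the lymph-node comparison.

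It would also go too far to say that group sizes will fall below plan. Protocol 5.2.2.1.1 freezes enrolment at 50 per age stratum and group without saying whether undosed subjects count. A shortfall is possible, not established.

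**What to change.** Align the synopsis, protocol section 3 and SAP 4.2 with Table 4, SAP Table 10 and protocol 5.2.2.1.1: randomisation takes place at Visit 1 only, after the eligibility re-check and the pre-vaccination checks, and immediately before vaccination. In SAP 3.1, reverse the order so that baseline blood is drawn before the group is allocated. No new reporting table is needed, because SAP 5.1 and 7.2.1 already show by group who was not vaccinated.

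The cost is a wording amendment to the protocol and SAP. No visit or procedure is added, since the staff who give the vaccine already access the randomisation system. The practical downside is that doses cannot be assigned to subjects some days ahead.

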#### **4.3 Data Handling**

##### Analysis Visit Names for Immunogenicity Analysis

Study visits will be derived as in Table 1. Analysis Visit names (AVISIT) will be used within the Immunogenicity Analysis. The primary endpoints are based on titer results 1 month after last vaccination so Visit 4 results are used for all study groups with the exception that the Visit 2 results for the MenACWY group will be used for the primary endpoints. The secondary endpoints are based on hSBA titer results 1 month after first vaccination so the MenACWY study group is excluded from the secondary endpoint analyses, since this group has only one visit where vaccine is administered.

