## 2. OBJECTIVES

### 2.1. Primary objective

- To assess the immune response to 2 doses of MenABCWY, rMenB+OMV NZ, or rMenB+OMV NZ and MenACWY administered concomitantly in the same arm or in 2 different arms, and to a single dose of MenACWY at 1 month after the last vaccination.

Refer to Section 10.1 for the definition of the primary endpoint.

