## CONFIDENTIAL

208205 MENABCWY-016 (V102\_19)  
Protocol Amendment 2 Final**Table 9** Study vaccines

Treatment name	Vaccine name	Formulation	Presentation	Volume to be administered	Number of doses
MenABCWY	MenACWY lyo	MenA=10µg,CRM197=16.7-33.3µg; MenC=5µg,CRM197=7.1-12.5µg; MenW=5µg,CRM197=3.3-8.3µg; MenY=5µg,CRM197=5.6-10µg; NaH 2 PO 4 =0.328mg; Sucrose=12.5mg	Lyophilized component in a vial	0.5 mL	2
	rMenB+OMV NZ	rp936-741=50µg; rp287-953=50µg; rp961c=50µg; OMV NZ98/254=25µg; Al(OH) 3 =1.5mg; Histidine=776µg; NaCl=3.125mg; Sucrose=10mg; Water=0.5mL	Suspension for injection in a pre-filled syringe		
rMenB+OMV NZ	rMenB+OMV NZ	rp936-741=50µg; rp287-953=50µg; rp961c=50µg; OMV NZ98/254=25µg; Al(OH) 3 =1.5mg; Histidine=776µg; NaCl=3.125mg; Sucrose=10mg; Water=0.5mL	Suspension for injection in a pre-filled syringe	0.5 mL	2
MenACWY	MenA lyo	MenA=10µg,CRM197=16.7-33.3µg; KH 2 PO 4 =5mM; Sucrose=12.5mg	Lyophilized component in a vial	0.5 mL	1 or 2
	MenCWY liquid	MenC=5µg,CRM197=7.1-12.5µg; MenW=5µg,CRM197=3.3-8.3µg; MenY=5µg,CRM197=5.6-10µg; NaCl=4.5mg; Na 3 PO 4 =10mM; NaH 2 PO 4 =2.5mM; Na 2 HPO 4 =7.5mM; Water=0.5mL	Liquid component in a vial		

Note: MenACWY is approved in adults as a single dose injection. In this study, for study groups rMenBOMV+ACWY\_S and rMenBOMV+ACWY\_D, 2 injections of MenACWY will be administered.

The Quality Control Standards and Requirements for each vaccine are described in separate Quality Assurance documents (e.g. certificate of analysis) and the required approvals have been obtained.

The vaccines are labelled and packed according to applicable regulatory requirements.

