- c. The difference in immune response compared to control groups in rMenBOMV+ACWY\_S versus rMenBOMV and MenACWY, rMenBOMV+ACWY\_D versus rMenBOMV and MenACWY, and MenABCWY versus rMenBOMV and MenACWY study groups, by serogroup A, C, W-135, Y, and B test strains.

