## 10.2. Secondary endpoints

### Immunogenicity Endpoints

- Immune responses against *N. meningitidis* serogroup B\* test strains and *N. meningitidis* serogroups A, C, W-135, and Y, as measured by hSBA, 1 month after the first vaccination in all groups (except for subjects in the MenACWY group)
  - hSBA GMTs against each of the *N. meningitidis* serogroup B test strains and against *N. meningitidis* serogroups A, C, W-135, and Y
  - hSBA GMTs against all of *N. meningitidis* serogroup B test strains (pooled)
  - Percentage of subjects with hSBA titers  $\geq$  the LLOQ against each of the *N. meningitidis* serogroup B test strains and against *N. meningitidis* serogroups A, C, W-135, and Y
  - Percentage of subjects with a 4-fold increase in hSBA titers against *N. meningitidis* serogroups B test strains and against *N. meningitidis* serogroups A, C, W-135, and Y
  - hSBA GMRs against each of the *N. meningitidis* serogroup B test strains and against *N. meningitidis* serogroups A, C, W-135, and Y at 1 month after the first vaccination against baseline (Day 1)

\*Serogroup B tests strains that will be tested are M14459 (fHbp), 96217 (NadA), NZ98/254 (PorA), and M07-0241084 (NHBA).

Notes, as described in Section 10.1, also apply to the secondary endpoints.

The ratios of GMTs between study groups will be analyzed to evaluate effect of treatment as described below:

- a. Immune interference due to stress to lymph nodes (lymph-node effect) in rMenBOMV+ACWY\_S versus rMenBOMV+ACWY\_D study groups, on the pooled B strains, and individually by serogroup A, C, W-135, Y, and B test strains.
- b. Other unknown interference in MenABCWY versus rMenBOMV+ACWY\_S study groups, by serogroup A, C, W-135, Y, and B test strains.
- c. The difference in immune response compared to control groups in rMenBOMV+ACWY\_S versus rMenBOMV, rMenBOMV+ACWY\_D versus rMenBOMV, and MenABCWY versus rMenBOMV study groups, by serogroup B test strains.

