##### **Full Analysis Set 2**

- All subjects in the All Exposed Set who provided evaluable serum samples and whose assay results are available for at least 1 serogroup or B strain at Visit 2 for all study groups except the MenACWY group.

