### 8.1.2 Secondary Endpoint

The analyses described in Section 8.1.1 will be repeated using AVISIT 2 instead of AVISIT 4, with the exception that the contrasts defined in Table 7 will be calculated (instead of Table 6). The MenACWY study group is not included in the secondary analyses.

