#### **8.3.2 Secondary Endpoint**

This endpoint will be summarized for PPS4.

The percentage of subjects with titers above the LLOQ as well as the associated 2-sided 80% Clopper-Pearson CIs [Clopper, 1934] will be computed by study group at AVISIT 2. Note that the MenACWY group is not included in the secondary analysis.

In addition, differences in percentages of subjects with titers above the LLOQ and 2-sided 80% CIs between selected study groups will be calculated using the method of Miettinen and Nurminen [Miettinen, 1985]. The following differences will be calculated:

- rMenBOMV+ACWY\_S versus rMenBOMV+ACWY\_D (test for immune interference, due to immunological stress to lymph node)
- MenABCWY versus rMenBOMV+ACWY\_S (test for other unknown immunological interference)
- rMenBOMV+ACWY\_S versus rMenBOMV
- rMenBOMV+ACWY\_D versus rMenBOMV
- MenABCWY versus rMenBOMV

No adjustments will be made for multiple comparisons.

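### No planned contrast with MenACWY alone is dose-matched for A, C, W-135 and Y: two doses are compared with one, and the one-dose-each comparison at Day 31 is left out although the serum is assayed

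*SAP*

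**What the plan says.** S and D below are the groups given rMenB+OMV NZ and MenACWY in the same arm and in different arms.

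**Doses.** MenACWY alone is one injection at Visit 1. For S and D, the note to Table 9 in protocol 6.1 says that "2 injections of MenACWY will be administered". MenABCWY is also given twice. The difference is declared: the primary objective (protocol 2.1) covers the two-dose regimens "and to a single dose of MenACWY at 1 month after the last vaccination".

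**Primary contrasts.** Contrast c in protocol 10.1 includes "MenABCWY versus rMenBOMV and MenACWY study groups, by serogroup A, C, W-135, Y, and B test strains", and the same for S and D. SAP Table 4 maps Visit 4 (Day 91) to AVISIT 4 for every group except MenACWY, whose Visit 2 (Day 31) takes that label. SAP Table 6 is computed at AVISIT 4.

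**Day 31.** Protocol 10.2 defines the secondary endpoint as responses "1 month after the first vaccination in all groups (except for subjects in the MenACWY group"). SAP 4.3 explains that "the MenACWY study group is excluded from the secondary endpoint analyses, since this group has only one visit where vaccine is administered". The exclusion recurs in SAP 8.1.2 ("The MenACWY study group is not included in the secondary analyses") and SAP 8.3.2 ("Note that the MenACWY group is not included in the secondary analysis"). Full Analysis Set 2 requires results "at Visit 2 for all study groups except the MenACWY group", and Full Analysis Set 4 makes the same exception.

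**Serum.** Protocol Table 6 has MenACWY subjects bled at Visits 1 and 2. Protocol Table 8 assays all eight components in about 500 subjects at Visit 2; its footnote removing MenACWY applies only to Visit 4.

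**The concern.** The study asks whether giving the antigens together depresses the response, and the design rationale promises a comparison with either vaccine alone. For serogroup B that control is dose-matched: rMenBOMV has two doses at Day 91 and one at Day 31, like the groups compared with it. For A, C, W-135 and Y, the MenACWY control is dose-matched in no planned contrast.

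S versus D and MenABCWY versus S are dose-matched on these serogroups, but every group in them also receives the B vaccine. If the B component lowers ACWY responses similarly in all three regimens, neither contrast can show it. Only MenACWY alone can, and the planned comparison with it mixes any such reduction with the effect of a second dose. A Table 6 ratio near or above 1 could then be read as absence of ACWY interference when it is not evidence of that.

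The stated reason does not support the exclusion. For a single-dose group the first and last vaccination coincide, so its Day 31 sample meets the timing of both endpoints.

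**Working it through.** **1. The plan's own figure.** Protocol Table 14 gives power 0.796 for 100 per group, difference −0.130 log10, SD 0.435 and one-sided alpha 10%. The noncentrality is 0.130 / (0.435 × √(2/100)) = 0.130 / 0.0615 = 2.11. Against a critical t of 1.286 on 198 df the power is 0.796, as stated. That figure concerns pooled B, S versus D, and nothing below alters it.

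**2. ACWY doses received before each sample** (protocol 3 and 6.1; SAP Table 4)

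| Group | At Day 31 | At the sample labelled AVISIT 4 |
|---|---|---|
| MenABCWY | 1 | 2 (Day 91) |
| S | 1 | 2 (Day 91) |
| D | 1 | 2 (Day 91) |
| MenACWY | 1 | 1 (Day 31) |

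**3. Contrasts on A, C, W-135 and Y** (SAP Tables 6 and 7)

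| Contrast | Day 31 | AVISIT 4 |
|---|---|---|
| S vs D | planned, 1 vs 1 | planned, 2 vs 2 |
| MenABCWY vs S | planned, 1 vs 1 | planned, 2 vs 2 |
| S, D and MenABCWY, each vs MenACWY | not planned (would be 1 vs 1) | planned, 2 vs 1 |

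**4. What the ratios estimate.** Let c be an ACWY ratio to MenACWY alone, at equal doses, that is common to the three regimens. Let k be the fold effect of the second dose.

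- S/D = c/c = 1.00 and MenABCWY/S = c/c = 1.00, whatever c is.
- Each Table 6 ratio against MenACWY = c × k.

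The documents give neither c nor k for these serogroups. As illustration only, c takes the 0.74 and 0.64 that protocol 10.4 reports for serogroup B, and k is varied:

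| c | k = 1.0 | 1.25 | 1.35 | 1.5 | 2 | k that hides c fully |
|---|---|---|---|---|---|---|
| 0.74 | 0.74 | 0.93 | 1.00 | 1.11 | 1.48 | 1/0.74 = 1.35 |
| 0.64 | 0.64 | 0.80 | 0.86 | 0.96 | 1.28 | 1/0.64 = 1.56 |

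**5. Chance that the Table 6 80% CI lies wholly below 1 when c = 0.64.** This is the probability that a noncentral t (198 df, noncentrality log10(0.64k) / (SD × √(2/100))) falls below −1.286. The documents give no SD for A, C, W-135 or Y. The values used are the 0.435 quoted for averaged B strains, and 0.6 and 0.8 as assumptions.

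| SD (log10) | k = 1 | 1.2 | 1.35 | 1.56 | 2 |
|---|---|---|---|---|---|
| 0.435 | 0.97 | 0.72 | 0.40 | 0.10 | 0.001 |
| 0.6 | 0.84 | 0.53 | 0.30 | 0.10 | 0.006 |
| 0.8 | 0.67 | 0.39 | 0.24 | 0.10 | 0.013 |

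**6. What Day 31 could show.** The 80% CI factor is 10^(1.286 × SD × √(2/100)) at 100 per group. For SD 0.435, 0.6 and 0.8 it is 1.20, 1.29 and 1.40, so an observed ratio below about 0.83, 0.78 or 0.72 (the reciprocals) would have its upper limit under 1. Power at one-sided 10% for a true 0.74 (−0.130 log10) is 0.80, 0.60 and 0.45. For 0.64 it equals the k = 1 column above, because dose no longer enters. At 90 per group the factors are 1.21, 1.30 and 1.42, and power for 0.74 is 0.76, 0.57 and 0.42.

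**7. Number of missing contrasts.** 3 groups × 4 serogroups = 12 for each of GMT, GMR, percentage at or above LLOQ and 4-fold rise: 48 outputs. The GMR model regresses change on the same baseline covariate as the GMT model, so its group differences are identical, leaving 36 distinct results.

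**The case against.** The strongest reply is that this is a declared regimen comparison. The primary objective names a single dose of MenACWY, protocol 6.1 notes that a single dose is the approved adult use, and protocol and SAP agree. This stands: Table 6 is valid as a comparison of regimens, and there is no conflict between the documents. It does not let those contrasts isolate interference.

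Second, the hypothesis, sample size and declaration rule concern serogroup B and S versus D. All analyses are descriptive, and nothing in the documents suggests uniform ACWY suppression, including when the vaccines go in different arms. This limits the consequence, but contrast c still asks the question for A, C, W-135 and Y.

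Third, the information is largely recoverable. The outputs give n, GMT and GSD for each group at Day 31, so an unadjusted ratio with a CI could be worked out by hand. That is correct. However, it would be post hoc, unadjusted for baseline, age stratum and center, and assembled from two outputs (PPS3 for MenACWY, PPS4 for the others).

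Fourth, the protocol synopsis says secondary comparisons match the primary ones, and protocol 10.8 lists the MenACWY contrasts without a time point. Read alone, these might seem to cover Day 31, but protocol 10.2 and the SAP rule it out.

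Finally, c, k and the SD are assumed, and the per-protocol sets will hold fewer than 100 if any subject is excluded. A, C, W-135 and Y also come last in assay priority when serum is short. The widths at 100 per group are therefore somewhat optimistic.

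**Conclusion.** The concern holds and should be fixed. All three planned GMT contrasts with MenACWY on A, C, W-135 and Y compare two doses with one, and the comparison at one dose each is excluded for a reason that does not apply. Twelve dose-matched GMT contrasts are missing, or 36 distinct results across all measures.

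How much could be hidden depends on a second-dose effect that the documents do not give: full masking needs at least 1.35-fold for a ratio of 0.74 or 1.56-fold for 0.64, smaller effects mask in part, and no effect masks nothing. The two ratios are borrowed from serogroup B, and the calculation assumes that the interference and second-dose effects multiply.

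This is an avoidable gap in interpretation. The pooled-B S versus D test, its declaration rule and the sample size are untouched.

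**What to change.** 1. In SAP 4.3 and Table 4, map the MenACWY Visit 2 sample to AVISIT 2 as well as AVISIT 4.
2. Admit MenACWY to FAS2 and FAS4, and so to PPS2 and PPS4 (SAP 4.4.4; protocol 10.5.4).
3. Add S, D and MenABCWY versus MenACWY on A, C, W-135 and Y to SAP Table 7 and to the comparisons in 8.3.2 and 8.4.2. Section 8.2.2 follows through Table 7. Remove the exclusion statements in 8.1.2, 8.2.2 and 8.3.2.
4. Align the secondary endpoint and contrast c (protocol synopsis and 10.2; SAP 3.2.2) and the secondary immunogenicity objective in section 2.2 of both documents.
5. Label the Table 6 MenACWY rows as two-dose versus single-dose regimen.
6. Keep S versus D and MenABCWY versus S at Day 91 as planned. Report the Day 31 MenACWY contrasts beside them, as the dose-matched reading against ACWY alone.

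The cost is a short amendment to both documents and some further descriptive contrasts without multiplicity adjustment. Vaccination, visits, subjects, samples and assays stay as they are. One limit remains: Day 31 cannot show interference that arises only after the second dose, and the report should say so.
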